2 BACKGROUND

2.1 REGULATORY HISTORY

A Phase III clinical study conducted under IDE G100240 was a 600 eye prospective, randomized, controlled, multi-center clinical trial of the LAL and LDD designed to evaluate safety and effectiveness over a 12-month period conducted at 17 sites. In addition to the visual correction of aphakia, reduction in residual spherocylindrical refractive error and improvement in uncorrected visual acuity were evaluated following LAL implantation and subsequent refractive adjustment of the LAL by the LDD.

Eyes with \geq 0.75 and \leq 2.5 diopters (D) of keratometric cylinder were randomly assigned to receive either the LAL or a commercially available, posterior chamber, non-accommodating, control monofocal IOL. Six hundred eyes were implanted with 403 eyes randomized to the LAL group and 197 eyes to the Control group.

Co-primary effectiveness endpoints included percent reduction in manifest cylinder, percent mean absolute reduction in manifest refraction spherical equivalent (MRSE), and rotation of the LAL. All primary effectiveness endpoints compared pre-adjustment (LAL) or 17-21 days (Control) to 6 months postoperatively and the first two endpoints compared results between the LAL and Control groups. All three co-primary effectiveness endpoints were met with a p-value <0.0001. The difference in means for percent reduction in manifest cylinder was 54.7%, with a p-value <0.0001. The difference in means for percent reduction in absolute MRSE was 41.1% with a p-value <0.0001. Rotation of the LAL of ≤5 degrees was observed in 96.1% of LAL implanted eyes with both the upper and lower bound of the 95% confidence interval exceeding the requirement of 90%.

100% of eyes in both the LAL and Control groups had BSCVA of 20/40 or better, exceeding the historic grid rate of 92.5% (ISO 11979-7). The incidence of sight-threatening complications and adverse events for the LAL and Control groups were also below the threshold rates calculated from the 1-year historical grid for intraocular lenses (ISO 11979-7, Ophthalmic implants-Intraocular lenses- Part 7: Clinical investigations) except for the category of Secondary Surgical Interventions (SSI), which was significantly higher than the historical rate (p<.05).

On November 22, 2017, the Center for Devices and Radiological Health (CDRH) of the Food and Drug Administration (FDA) approved RxSight's premarket approval application (PMA) for the Light Adjustable Lens (LAL) and Light Delivery Device (LDD) system. The approval order included a requirement to conduct a post-approval study to evaluate the following postmarket questions:

- 1. What is the rate of Endothelial Cell Density loss (ECL) for patients with the LAL/LDD?
- 2. What is the rate of retinal damage caused by UV treatment with the LDD that may not be detected by routine post-operative testing?

The objective of this study is to address both of the postmarket safety questions.

Phase A of the study is designed to develop and validate a patient-reported outcome measure for erythropsia, the "Daily Life Erythropsia Questionnaire" (DLEQ). As this PRO instrument will be used in RxSight Investigational Device Exemption applications for the LAL and LDD as well as in Phase B of this post-approval study, RxSight submitted a Pre-Submission which provided the study protocol for development of the DLEQ to FDA on January 12, 2018 (LLEQ). As this development work is being conducted outside of the United States where the LAL and LDD are commercially available, the Pre-Submission process was thought to be the best regulatory mechanism for receiving feedback regarding the proposed development plan.

The Phase A study was completed, submitted to FDA in P160055/R003 and approved by FDA on October 24, 2019.

2.2 DEVICE DESCRIPTION

RxSight's Light Adjustable Lens (RxSight LAL) is a silicone intraocular lens whose shape and focusing characteristics can be modified after implantation using an office-based UV light source, the RxSight Light Delivery Device (LDD), to improve uncorrected distance visual acuity.

2.2.1 RXSight Light Adjustable Intraocular Lens

The RxSight LAL is a posterior chamber, UV absorbing, three-piece, foldable, photoreactive silicone intraocular lens with a squared posterior optic edge intended to be implanted in the capsular bag following phacoemulsification. Selective exposure of the implanted RxSight LAL using the LDD to deliver spatially profiled UV light produces modifications in the lens curvature resulting in a spherical or spherocylindrical power change post-operatively. A subsequent locking exposure is delivered to the implanted RxSight LAL to stabilize the lens power.

Lens Optic

- Material: Photo-reactive UV absorbing Silicone
- Light transmission: UV cut-off at 10% T ≥392 nm for all lens powers
- Index of refraction: 1.43
- Diopter power: +4.0 to +15.0 diopters and +25.0 to +30.0 D in 1.0 diopter increments; +16.0 to +24.0 diopters in 0.5 diopter increments
- Optic type: Biconvex

Optic edge: Square on posterior surface and round on anterior surface

Overall diameter: 13.0 mmOptic diameter: 6.0 mm

Haptics

• Configuration: Modified C

• Material: Blue core polymethylmethacrylate

Haptic angle: 10°

[figure not shown]

FIGURE 1: RXSIGHT LIGHT ADJUSTABLE LENS

FIGURE 2: RXSIGHT LIGHT ADJUSTABLE LENS. INSET DEPICTS BACK LAYER.

The RxSight LAL silicone material is designed to respond to a narrowband UV light of a select spatial intensity profile. The silicone material contains photoreactive additive, which is selectively photo-polymerized in targeted areas upon exposure to the near UV light to alter the lens shape thus modifying spherical and spherocylindrical power of the RxSight LAL.

2.2.2 LIGHT DELIVERY DEVICE (LDD)

The Light Delivery Device is a digital UV light projection system used to induce a predictable change in the RxSight LAL power after implantation. The LDD consists of an anterior segment biomicroscope with the addition of an optical projection system, electronic control circuitry, and a UV source. The LDD device can treat postoperative manifest cylinder from -0.50 D to -2.00 D, and manifest sphere (in minus cylinder format) of -2.00 D to +2.00 D.

2.3 INDICATIONS FOR USE

The Light Adjustable Lens and Light Delivery Device system is indicated for the reduction of residual astigmatism to improve uncorrected visual acuity after removal of the cataractous natural lens by phacoemulsification and implantation of the intraocular lens in the capsular bag, in adult patients:

- With pre-existing corneal astigmatism of ≥ 0.75 diopters
- Without pre-existing macular disease.

The system also reduces the likelihood of clinically significant residual spherical refractive errors.

3 STUDY OBJECTIVE

The primary objective of this study is to conduct a post-approval study which evaluates the following two safety questions:

- 1. What is the rate of Endothelial Cell Density loss (ECL) for patients with the RxSight LAL/LDD?
- 2. What is the rate of retinal damage caused by UV treatment with the LDD that may not be detected by routine post-operative testing?

4 STUDY DESIGN

This is a two phased study that will include Phase A (complete) and Phase B.

Phase A

The primary objective of Phase A was to develop a patient-reported outcome (PRO) instrument that assessed erythropsia after LDD light treatments, the "Daily Life Erythropsia Questionnaire" (DLEQ). This was a non-interventional, cross-sectional study at 1-3 sites with primary data collection from patients who had undergone cataract surgery with implantation of the RxSight LAL and had treatment performed with the Light Delivery Device. Phase A was designed to use approximately English speaking patients at sites in the European Union where the device has a CE Mark.

Qualitative research interviews were conducted with adult patients who reported experiencing erythropsia to their eye care provider after treatment with the Light Delivery Device. These patients were identified, invited to participate, and interviewed within 8 weeks of a report of the erythropsia symptom. Cognitive debriefing methods were used during the interviews: (1) to ensure the questionnaire captures relevant aspects of erythropsia from the patient perspective, (2) to evaluate the clarity of each question, and (3) to assess response options for each question to ensure options capture the range of patient experiences (e.g., frequency, light conditions). Cognitive interviews and qualitative coding were to be conducted in up to three rounds of interviews and analysis with about eight patients per round. This allowed an iterative approach to

the cognitive interviews and instrument modification: the DLEQ was tested with patients in the first round of interviews; following participant feedback modifications were made to the DLEQ; the revision was tested in the second round of patient interviews; based on participant feedback adjustments were made to the instrument. An optional third and final round of interviews was determined not to be need as further as further changes were not required. The instrument was revised to incorporate patients' words to support its content validity and to increase the clarity and understandability of items that will be used to assess patient experiences with erythropsia.

There will be no assessments of treatment effectiveness or safety associated with the phase for PRO development. There were no laboratory assessments associated with this research. This protocol was submitted to an Institutional Review Board(s)/Ethics Committee as required for studies with primary data collection from patients.

Patients treated in a commercial setting were evaluated using the following inclusion/exclusion criteria.

INCLUSION CRITERIA

- Adult patients (40 to 80 years of age) that had implantation of the RxSight Light Adjustable Lens (LAL™).
- Patient reported experiencing erythropsia to their eye care provider after treatment with the Light Delivery Device within the past eight weeks.
- Patient is able to read, write, speak, and understand English.
- Patient is willing and able to comprehend and sign a written informed consent prior to study entry.

EXCLUSION CRITERIA

- Patient has a clinically-relevant medical or psychiatric condition which, in the opinion of
 the investigator and/or coordinator, would interfere with completing the study including,
 but not limited to, sensory problems, cognitive impairment, acute mental illness or
 inadequately treated depression or anxiety.
- Complications during cataract surgery that would complicate evaluation of the erythropsia symptom.

Phase B

Phase B is a prospective, randomized, controlled, multicenter, post approval study of the RxSight LAL and LDD to be conducted at up to 15 clinical sites. It will begin after development of the "Daily Life Erythropsia Questionnaire" PRO is complete and has been accepted by FDA. This is a new enrollment study that includes up to 12 study visits. Subjects will be randomized in a 2:1 ratio to receive either the RxSight LAL or a monofocal IOL (Control).

Patients who require cataract extraction and intraocular lens implantation will be screened for eligibility. If it is determined that the patient may be eligible to participate, study staff will explain the study purpose, procedures, risks/benefits and subject responsibilities to the potential

participant. Written informed consent will be obtained prior to any study specific testing. The patient is enrolled upon signing the informed consent.

Subjects with preoperative corneal astigmatism of ≥0.75 D, without pre-existing macular disease, and meeting all inclusion/exclusion criteria will be randomly assigned in a 2:1 ratio to receive either the RxSight LAL or a commercially available monofocal IOL (Control).

Commencing at the Postop Week 3 visit, eyes will be refracted and undergo visual testing. Eyes implanted with the RxSight LAL will receive a power adjustment based on the manifest refraction. Eyes measured with a manifest cylinder of ≥ 0.50 D will receive a sphero-cylindrical treatment while eyes with <0.50 D of manifest cylinder will receive only a spherical treatment. Subjects implanted with the RxSight LAL will return 3 to 7 days after their first adjustment and the same measurements performed again.

Subjects will receive one to three adjustments and up to two lock-in treatments. All light treatments are separated by 3 to 7 days.

Postoperatively, all subjects will undergo complete ophthalmic examinations at regular intervals over a 6-month period. Masked examiners will be utilized at postop week 3 and postop month 6 to perform visual acuity and manifest refraction measurements. If a study eye is diagnosed with UV retinal damage, an additional follow-up exam will be added at 12 months postoperatively to confirm resolution or document sequelae, if any.

5 OUTCOME PARAMETERS

5.1 EFFECTIVENESS PARAMETER

The primary effectiveness endpoints are:

- Mean absolute manifest refraction spherical equivalent ([MRSE]) at postop month 6 compared between the RxSight LAL and Control group
- Mean manifest cylinder at postop month 6 compared between the RxSight LAL and Control group

The comparisons will be made by descriptive statistics only.

[figure not shown]
5.2 SAFETY PARAMETERS

The primary safety endpoints are:

- Median rate of endothelial cell density loss at postop month 6 compared to preoperatively compared between the LAL and Control group
- Percent of LAL eyes with UV retinal damage at postop month 6

Other Key Safety parameters

- Rates of erythropsia at each visit beginning at Postop Week 3, as evaluated by the inoffice erythropsia assessment, in RxSight LAL eyes
- Rates of erythropsia at each visit beginning at Postop Week 3, as evaluated by the Daily Life Erythropsia Questionnaire (DLEQ), in RxSight LAL eyes
- Rates of tritan anomaly on the City University Color Test at each visit beginning at Postop Week 3, in RxSight LAL eyes
- Rates of all types of adverse events, including loss of best corrected distance visual acuity (BCDVA) of ≥2 lines from Postop Week 3 visit, in RxSight LAL eyes
- In specular microscopy sub-study compared between the RxSight LAL and Control group:
 - Rate of within-eye loss of ≥25% ECD from preoperative visit at Postop Week 3 and Postop Month 6
 - Rate of within-eye loss of ≥30% ECD from preoperative visit at Postop Week 3 and Postop Month 6

6 STUDY POPULATION

The Phase B study will include 500 subjects who will be randomized 2:1 to receive either an RxSight LAL or a monofocal control IOL.

Subjects should be screened for eligibility and only eyes meeting all inclusion and none of the exclusion criteria will qualify for implantation.

6.1 Inclusion Criteria

- Must sign a written Informed Consent form and be willing to undergo cataract surgery for the implantation of an IOL with random assignment to either the RxSight LAL or the monofocal control IOL.
- Between the ages of 40 and 80 inclusive on the day the cataract surgery is performed.
- Preoperative corneal cylinder ≥0.75 D to ≤2.00 D or >2.00 D and ≤ 2.5 D of corneal cylinder with a steep axis between 70 degrees and 110 degrees.
- Study eye has best corrected distance visual acuity projected (by clinical estimate based upon past ocular history and retinal exam) to be 20/20 or better after cataract removal and IOL implantation.
- Study eye has clear intraocular media other than cataract.
- Willing and able to comply with the requirements for study specific procedures and visits.

- Study eye has average dilated pupil diameter of ≥7.0 mm.
- Able to complete a written questionnaire in English.
- Study eye requires an IOL power within the range available for the RxSight LAL.

6.2 EXCLUSION CRITERIA

- Study eye with pre-existing macular disease.
- Study eye with a history of uveitis.
- Study eye with comeal pathology or corneal dystrophy that is either progressive or sufficient to reduce BCDVA to worse than 20/20.
- Subjects with serious co-morbid conditions that in the judgment of the investigator makes
 inclusion in the study not in the best interest of the subject.
- Subjects taking systemic medication that may increase sensitivity to UV light such as
 tetracycline, doxycycline, psoralens, amiodarone, phenothiazines, chloroquine,
 hydrochlorothiazide, hypericin, ketoprofen, piroxicam, lomefloxacin, and methoxsalen.
 LDD treatment in patients taking such medications may lead to irreversible phototoxic
 damage to the eye. This is only a partial list of photosensitizing medications. Please
 evaluate all medications that the patient is taking for this effect prior to consideration for
 implantation.
- Subjects taking a systemic medication that is considered toxic to the retina such as tamoxifen.
- Study eye with history of ocular herpes simplex virus.
- Study eye with nystagmus.
- Study eye that has been compromised due to previous trauma or developmental defects in which appropriate support of the intraocular lens (IOL) is not possible.
- Study eye with current vitreoretinal disease or is at a high risk for future vitreoretinal disease that may require silicone oil as part of therapy.
- Study eyes where the posterior capsule nor the zonules are intact enough to provide support for the IOL.
- Study eyes where the investigator believes maintaining study fixation will not be possible.

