6.3 SUBJECT ENTRY

Patients who require cataract extraction and intraocular lens implantation will be screened for eligibility. If it is determined that the patient may be eligible to participate, study staff will explain the study purpose, procedures, risk/benefits and subject responsibilities to the potential participant. Written informed consent will be obtained prior to any study specific testing. The patient is enrolled upon signing the informed consent. The subject will sign and date the informed consent form in the presence of the person conducting the consent process. The investigator and/or the person conducting the consent process will also sign and date the consent form. The preoperative examination will be performed no more than 60 days prior to surgery. If the 60-day time period elapses, it is acceptable for patients to be re-screened by undergoing a complete preoperative examination.

Only subjects meeting all inclusion/exclusion criteria will be implanted. Those subjects who do not meet the inclusion/exclusion requirements will be considered screen failures. Subjects will continue to be enrolled until 500 subjects have been randomized and undergone implantation with the RxSight LAL or a monofocal IOL. If surgical complications occur and no LAL is implanted, the subject is exited from the study. Unique identification numbers will be assigned to each subject. The randomization schedules for each site will be prepared in advance and only the study statistician will have access to the randomization schedule. Prior to the surgical procedure, study site personnel will enter the subject's study ID into the study's EDC system and the treatment assignment (RxSight LAL or Control IOL) will be generated. Documentation of the randomization assignment for each subject will be maintained in the subject's file and in the EDC system.

The implant lens power for the RxSight LAL and the Control IOL will be calculated based upon the ocular biometry data and a standard IOL power calculation formula with the IOL closest to the post-surgical refractive target selected in an unbiased manner.

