6.4.2 LIGHT TREATMENT PROCEDURE

Seventeen (17) to 24 days after surgery, the subject will return for the Postop Week 3 evaluation and a 1st adjustment treatment of the RxSight LAL. Subsequent second and third adjustment treatments, if necessary, will all be separated by 3-7 days. The subject will receive the 1st lock-in treatment 3-7 days after the final adjustment treatment. If necessary, lock-in #2 may be performed 3-7 days after lock-in #1. Depending on the adjustment(s) performed, subjects will receive one to three adjustments and one or two lock-in treatments.

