6.4.2.1 Postponement of Light Treatment Procedure(s)

LDD treatment should be delayed if any of the following new symptoms or changes in performance are noted;

- Color Vision Testing: Treatment should be delayed if the subject scores worse on Part 2 of the City University Color Test than the Pre-adjustment test for Tritan evaluation.
- Erythropsia Evaluation: With any score of 2 (red), the treatment should be delayed.
- Best Corrected Distance Visual Acuity: With any loss of BCDVA (unless the cause is known to be non-retinal) of 10 letters or more on an ETDRS (logMAR) chart compared to the Postop Week 3 BCDVA, treatment should be delayed.

- 6.4.2.2 Requirements for Additional Testing

Additional testing should be performed as soon as possible to evaluate whether UV-related retinal damage has occurred if any of the following is observed. will be performed in eyes that meet any of the following criteria:

- Significant erythropsia during in office erythropsia assessment (score of 2 (red))
- Significant erythropsia as indicated on responses to the Daily Life Erythropsia Ouestionnaire including:
 - o "severe" or "very severe" erythropsia on question 3, OR
 - o a response of "very bothersome" erythropsia on question 6, OR
 - o a response of "more than 7 days" on question 2
- Significant crythropsia as interpreted by the investigator based on spontaneous reports by the subject
- If the subject reports any level of erythropsia at the Postop Month 1-2 visit OR at any interim visit after the Postop Month 1-2 visit and <90 days after surgery based on results of the in office erythropsia assessment, the Daily Life Erythropsia Questionnaire or spontaneous verbal reports by the subject, the subject will be mailed a paper version of the Daily Life Erythropsia Questionnaire to self administer and return to the investigational site between 90-120 days after surgery. If responses to the Daily Life

² Azar D, Stark W, Dodick J, et al. Prospective, randomized vector analysis of astigmatism after three-, one-, and no-suture phacoemulsification. J Cataract Refract Surg 1997; 23:1164-1173.

Erythropsia Questionnaire indicate that there is erythropsia on question 1, the subject should have an unscheduled visit and testing should be performed.

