6.4.2.3 Procedure Preparation

Protocol-required measurements should be completed prior to adjustment or lock-in treatments.

The subject should be prepared for light treatments as follows:

Once adequate pupil dilation is achieved, patch the subject's fellow eye and position the subject comfortably in front of the LDD with chin in the chinrest and forehead against the support bar. Ask the subject to grasp the handles on the LDD table for support. Inform the subject to concentrate on the green fixation light presented in front of them and to try and minimize eye movement.

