6.4.2.4 Adjustment Procedure(s)

Refer to the LDD Operator's manual for instructions on LDD start up and instructions for the daily alignment test to be performed prior to the first treatment of the day to ensure the UV beam is aligned to the reticle. If the UV beam is not aligned to the reticle within the specifications detailed in the LDD Operator's manual, do not perform treatments and call RxSight customer service immediately.

- 1. All adjustment procedure(s) will be recorded.
- 2. Within the Patient ID and Patient Data screens, follow the touchscreen prompts to enter requested information. Press the "Proceed" button once information has been entered respectively for each screen.
- 3. Within the Confirmation screen, review all information and press the "Confirm" button.
- 4. Verify that the LDD ring lights and reticle target are activated.
- 5. Apply topical anesthetic.
- 6. Position the RxSight supplied contact lens (M = 0.766x) on the cornea using hydroxypropyl methylcellulose as the coupling medium.

Note: The RxSight contact lens is similar to those used in other ophthalmic procedures in which customized magnification is required. To ensure correct magnification for treatment, use only the RxSight designated contact lens.

- 7. Instruct the subject to focus straight ahead on the LDD fixation light with the study eye.
- 8. Using the microscope, focus on the cornea and verify that there are no trapped bubbles present. Confirm alignment of the contact lens by approximately aligning the Purkinje images to the inner circle of the reticle target.
- 9. Using the microscope, focus on the RxSight LAL haptics and align the reticle target with the periphery of the RxSight LAL.
- 10. Press the "Ready" button
- 11. Initiate the UV exposure as prompted by the LDD display using the trigger. Use the joystick to keep the RxSight LAL centered in the alignment reticle.
- 12. Perform micro adjustments to keep the reticle target centered to the RxSight LAL and to keep the RxSight LAL in focus. In the case of subject movement, loss of alignment, or loss of focus, pause the treatment, quickly refocus, realign the lens with respect to the reticle beam, and immediately resume treatment to limit the duration of any pauses once the light treatment has been initiated.

Note: Always maintain the RxSight LAL in focus by focusing at the haptics. Never focus onto the CCC (capsulotomy) or Purkinje images.

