- 13. If the event of an aborted Adjustment Treatment, do not initiate a new treatment sequence; instead; instruct the subject to return 3-7 days later for refractive evaluation to assess whether an adjustment treatment is required or to proceed directly to a lock-in treatment.
- 14. Following the light adjustment, the subject will continue to wear their UV protective eyewear as instructed until exactly 24 hours after the final lock-in treatment has been completed.

The subject will return 3 to 7 days following the power adjustment treatment for another light treatment. The subject may receive up to 3 adjustment treatments before receiving the 1st lock-in treatment.

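### Section 6.2 warns of irreversible damage from LDD light in patients on photosensitising drugs, but no readable text tells the site to withhold light if such a drug is started after surgery

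*Combined protocol and SAP*

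**What the plan says.** Section 6.2 excludes subjects taking systemic drugs that raise sensitivity to UV light. It names doxycycline, hydrochlorothiazide, amiodarone and others, calls the list partial, and gives the reason: "LDD treatment in patients taking such medications may lead to irreversible phototoxic" damage to the eye. The investigator is asked to "evaluate all medications that the patient is taking for this effect prior to consideration for" implantation. A separate criterion excludes drugs toxic to the retina, such as tamoxifen.

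The light is scheduled later. Section 6.4.2 states: "Seventeen (17) to 24 days after surgery, the subject will return for the Postop Week 3 evaluation and a 1st adjustment treatment". Up to two more adjustments and one or two lock-ins follow, each 3 to 7 days after the last.

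Section 6.4.2.1 sets out when to postpone: "LDD treatment should be delayed if any of the following new symptoms or changes in performance are noted". Three items follow: a worse tritan result on the colour test, an erythropsia score of 2, and a loss of 10 or more letters of best corrected acuity not known to be non-retinal. Section 6.4.2.3 adds that "Protocol-required measurements should be completed prior to adjustment or lock-in treatments". Table 1 in section 6.7 marks medication history at every visit, including Postop Week 3, Adjustments #2 and #3, and both lock-ins.

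**The concern.** The hazard in 6.2 is tied to the light, but the stated check is tied to the implant. A subject who is free of these drugs at screening and is then prescribed one during recovery meets the condition that the warning describes, at the visit where the exposure is given. The site will have the drug on its updated medication record, but no readable instruction says what to do about it.

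What is at stake is first the subject's retina, since the protocol itself calls the possible damage irreversible. It also touches a primary safety endpoint, the percentage of LAL eyes with UV retinal damage at Month 6 (section 5.2).

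**Working it through.** **When light is given.** The protocol prints the intervals but no last day, so I added them up from 6.4.2 and 6.6. Earliest day: 17, plus 3 for each further session. Latest day: 24, plus 7 for each further session.

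| Session | Earliest day | Latest day |
|---|---|---|
| Adjustment #1 | 17 | 24 |
| Adjustment #2 | 17 + 3 = 20 | 24 + 7 = 31 |
| Adjustment #3 | 20 + 3 = 23 | 31 + 7 = 38 |
| Lock-in #1 after three adjustments | 23 + 3 = 26 | 38 + 7 = 45 |
| Lock-in #2 | 26 + 3 = 29 | 45 + 7 = 52 |

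The shortest course, one adjustment and one lock-in, ends between Day 17 + 3 = 20 and Day 24 + 7 = 31. Light therefore runs from Day 17 to at most Day 52 on schedule. A postponement under 6.4.2.1 could move it later.

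**What the readable light-visit text acts on.**

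- 6.4.2.1: colour score, erythropsia and acuity. A new drug is neither a symptom nor a change in performance.
- 6.4.2.2: triggers for additional testing, all based on erythropsia, tritan score or acuity.
- 6.4.2.3: measurements come before treatment, with no action attached to the medication record.
- 6.4.2.4 and 6.4.2.5: if the UV beam is out of alignment, "do not perform treatments and call RxSight customer service immediately". After an aborted adjustment, no new sequence is started that day. After an aborted lock-in, the site contacts the sponsor.

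None of these mentions a drug. The beam rule does show that the protocol is willing to place a preventive rule at the light visit, before any symptom.

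**Whether the symptom rules could stand in.** At Adjustment #1 the colour item compares with the pre-adjustment test and the acuity item with Postop Week 3. Adjustment #1 is given at Postop Week 3, so those two measurements are the reference and cannot yet show a change. Only the erythropsia item can act at that visit. At later visits all three can act, but by then at least one UV exposure has been given.

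**An illustrative case.** A subject starts doxycycline on Day 10. Adjustment #1 follows 17 − 10 = 7 to 24 − 10 = 14 days later. Section 6.9.4 does not allow withdrawal after implantation while the lens is in place, so the exclusion criterion no longer removes this subject. Without symptoms, no readable rule delays the light.

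**The case against.** The strongest reply is that the rule may exist where it cannot be read. The reference in 6.7 for assessment techniques, which would govern medication history, is missing. Part of 6.4.2.2 is damaged. The LDD Operator's manual, to which 6.4.2.4 and 6.4.2.5 defer for start-up and alignment, is not supplied. This stands. Missing text is not an omission from the plan, so a reader should not infer that the trial has no such safeguard. The documents support only the narrower statement that none is readable and that 6.4.2.1 does not point to one.

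A second reply is that much of the control is already there. The 6.2 warning speaks of treatment with light, the medication list is updated at each light visit, assessments precede treatment, and section 8.2 expects the investigator to look after the subject's welfare. A careful investigator may well connect these. That lowers the likely frequency of the problem. It does not supply an instruction, and before implantation the protocol did not leave the same step to inference.

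Two stronger readings should be set aside:

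- A reader might count from the preoperative examination (6.3: "The preoperative examination will be performed no more than 60 days prior to surgery") and infer an unchecked gap of up to 60 + 24 = 84 days to first light, or 60 + 52 = 112 days to last light. Table 1 also records medications on the operative day, Postop Day 1 and Week 1, so those spans are not periods without information. The times from surgery are the fair ones.
- A reader might count the delay and do-not-treat rules and take the absence of a drug among them as a measure of the gap. Any such count depends on which equipment and procedure steps are included, and it measures nothing.

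**Conclusion.** The point holds for the readable text. The protocol ties possible irreversible damage to LDD light, states a medication check only before implantation, records medications at all five light visits, and links no readable action to a drug started after surgery. The exposure period is Day 17 to at most Day 52 on schedule, assuming the longest course with every interval at its upper limit and no postponement.

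The size of the problem in subjects cannot be given: the documents offer neither a rate of new prescriptions nor a risk of damage under them. The case for change rests on the severity that the protocol itself assigns to the harm and on the low cost of a rule that uses data already collected. Confidence is medium because of the unreadable text.

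**What to change.** Add to 6.4.2.1:

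> Before each adjustment and lock-in, review the updated medication history. If the subject is taking a systemic photosensitising or retinotoxic medication of the type excluded in 6.2, delay the light treatment and continue UV protective eyewear until the prescriber has stopped or substituted the drug and the investigator judges it has cleared. If it cannot be stopped, contact the sponsor before any light treatment. Such a delay may exceed the 3 to 7 day spacing or the Day 17 to 24 window. If Adjustment #1 is delayed, repeat the pre-light BCDVA, colour and erythropsia assessments on the day of treatment and use them as the pre-light reference.

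If the unreadable technique text or the manual already holds this rule, a cross-reference from 6.4.2.1 is enough.

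The repeat of the pre-light assessments matters because Postop Week 3 is the reference for later acuity, tritan and erythropsia changes, and a long delay would leave that reference out of date.

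The cost is one paragraph and a line on the light-visit worksheet. A few subjects would have a session rescheduled, a longer period in UV eyewear with an unlocked lens (possibly much longer for a long-term drug), and a repeated assessment. Short delays fit the schedule. On the longest course the Month 1-2 visit falls by Day 52 + 14 = 66, which leaves 120 − 66 = 54 days before the Month 6 window opens.
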